9.2 Dose rationale

The dose combination of 100mg bid epacadostat plus pembrolizumab for the ongoing phase III melanoma study is based upon a benefit/risk assessment made specifically in melanoma in collaboration with Merck. In the phase 1/11 study examining this combination, there was evidence of improved efficacy in melanoma subjects at all doses of epacadostat from 50 to 300mg bid. The same dose of the combination therapy of epacadostat and pembrolizumab will be use in this phase II study as is being used in the melanoma specific phase III study.

9.3 Duration of Therapy

Study treatment may continue until one of the following criteria applies:

Until a total of 35 cycles (approximately 2 years) of treatment has been administered as long as subjects are receiving benefit from treatment and have not had disease progression or met any criteria for study withdrawal outlined below

Clinical or radiographic disease progression as defined by RECIST 1.1. Patient may be allowed to continue treatment after progression if they are deriving clinical benefit (section 9.4).

Intercurrent illness that prevents further administration of treatment

Intolerance of study treatment

Patient decides to withdraw from the study

Physician decides to withdraw a patient from the study for a reason not listed here

Pregnancy in patient

The patient is lost to follow-up

Inability of the patient to comply with the requirement of the protocol for treatment or evaluation.

End of study, whichever occurs first.

9.4 Treatment Beyond Initial RECIST 1.1 Defined Progression of Disease

Due to the mechanism of action, subjects may experience growth in existing tumors or the appearance of new tumors prior to maximal clinical benefit of the combination therapy of epacadostat and pembrolizumab. The patient may be allowed to continue study treatment after initial RECIST 1.1 defined progression if they are assessed by the treating physician to be deriving clinical benefit and tolerating study treatment. The treating physician may consult with the overall study PI for help with assessing the patient. Patients who decide to continue study therapy on protocol after initial radiolgic evidence of disease progression will need to provide written informed consent at the time of the decision to treat beyond initial evidence of progression of disease on study therapy. Such patients should discontinue study therapy upon further evidence of progression at the discretion of the treating physician.

9.5 General Concomitant Medication and Supportive Care Guidelines

Supportive Care: Best supportive care and treatment will be given as appropriate to each subject as per Clinical Center and ASCO guidelines (antiemetics, antibiotics, packed red blood cell and platelet transfusions, nutritional support, non-radiation palliative treatment for pain).

Steroids: Doses up to 10mg of prednisone daily (or equivalent) will be allowed concurrently with continuous treatment with epacadostat and/or pembrolizumab.

If the subject requires corticosteroid dosing of >10 mg prednisone daily equivalent) and/or other (or immunosuppressive medication for related toxicities. epacadostat and pembrolizumab dosing must be held until the corticosteroid dose has decreased to 10 mg prednisone daily (or equivalent) and the administration of the other

immunosuppressive medication has discontinued. Higher doses of prednisone (.i.e., >10mg) may potentially be allowed in combination with the study therapy if they are prescribed for non-immune mediated indications at the discretion of the principal investigator.

Radiation: Radiation therapy are only allowed during the study if required

for palliation of symptoms due to underlying sarcoma.

Non-Surgical

Local Interventions:

study

Non-surgical local interventions are only allowed during the if required for palliative of symptoms due to underlying sarcoma

Surgery: Subjects must not schedule any elective surgeries during

the treatment period and for at least 30 days after the last administration of study drugs. If a subject undergoes any unexpected surgery or local intervention during the course of the study, all study treatments must be withheld and the investigator or designee should notify the sponsor' as soon as possible. A subject may be allowed to resume study drugs if both the investigator and sponsor's medical monitor agree to

restart study therapy

Other supportive measures and specific treatments/guidelines recommended for the management of toxicities are detailed in Appendix B.

9.6 Drug Interactions

9.6.1 Epacadostat

9.6.1.1 Restricted Medications/Treatment

- Systemic steroids may be used at doses 10 mg/day prednisone or equivalents. However, in the setting of non-immune mediated indications for use, chronic/active low dose steroid use at doses >10mg/day prednisone or equivalents, may be permitted at the discretion of the principal investigator.

Use of coumarin-based anticoagulants (eg, Coumadin) is discouraged. Low-dose Coumadin® (1 mg) is acceptable; however, doses that increase the INR are discouraged and will require dose modification. If an alternative to coumarin-based anticoagulants cannot be used, dose modifications of the Coumadin® may be needed. Based on the observed magnitude of epacadostat/warfarin PK interaction and PK/PD modeling results, for an epacadostat dose of 100 mg BID, the dose of

warfarin should be maintained and close INR monitoring is recommended. Based on PK/PD modeling, recommendations for warfarin dose modifications for subjects receiving epacadostat :s; 100 mg BID are summarized in Table 3 below based on the INR prior to starting epacadostat.

Table 3. Recommendations for Warfarin dose modification in setting of concomitant epacadostat

	Epacadostat Dose	
Stable Baseline INR	:S 100 mg BID	
INR ::;2.5	Close INR monitoring	
INR > 2.5	Close INR monitoring	

Use of the anticonvulsant carbamazepine (a UGT1A9 inducer) is discouraged.
 Because there is a potential interaction that could result in lower epacadostat exposures, an alternative to carbamazepine should be used, if possible.

9.6.1.2 Prohibited Medications/Treatment

Subjects are prohibited from receiving the following therapies starting from screening through end of treatment phase of this study unless otherwise noted below:

- Any investigational medication other than the study drugs.
- Use of any anticancer medications, including chemotherapy or biologic therapy other than the study medications.
- Any chronic immunological-suppressive treatment. (Note: Inhaled or topical steroids are allowed, and systemic steroids at doses:510 mg/day prednisone or equivalents are allowed and immune suppressants are allowed for short-term treatment for immune toxicities or as prophylaxis for contrast allergy for imaging procedures. Steroid use at doses >10mg/day prednisone or equivalents for nonimmune mediated indications may be permitted at the discretion of the principal investigator)
- Radiation therapy

Note: In the presence of a mixed response (some lesions improving or stable and other lesions progressing), radiation therapy to a symptomatic solitary lesion or to the brain is allowed.

 Administration of a live attenuated vaccine within 30 days before the first dose of study treatment and while participating in the study. Examples of live vaccines include, but are not limited to, the following: measles, mumps, rubella, chicken pox, yellow fever, rabies, BCG, and typhoid vaccine. Seasonal influenza vaccines for injection are generally killed virus vaccines and are allowed;

however, intranasal influenza vaccines (eg, FluMist®) are live attenuated vaccines and are not allowed.

- Use of any MAOI or drug associated with significant MAOI activity agents is prohibited from 21 days prior to Day 1 through 2 weeks after the final dose of epacadostat has been administered
- Use of any immunological-based treatment for any reason from screening through follow-up visit is prohibited.
 - Note: Completed adjuvant therapy (eg, vaccines) with medical monitor approval, inhaled or topical steroids, and systemic steroids at doses 10 mg/day prednisone equivalents are allowed, as described in Restricted Medications.
- Any UGT1A9 inhibitor, including acitretin, amitriptyline, androsterone, cyclosporine, dasatinib, diclofenac, diflunisal, efavirenz, erlotinib, estradiol (17-beta), flutamide, gefitinib, gemfibrozil, glycyrrhetinic acid glycyrrhizin, imatinib, imipramine, ketoconazole, linoleic acid supplements, mefenamic acid, mycophenolic acid, niflumic acid, nilotinib, phenobarbital, phenylbutazone, phenytoin, probenecid propofol, quinidine, ritonavir, sorafenib, sulfinpyrazone, valproic acid, and verapamil.

Subjects may receive other medications that the investigator deems to be medically necessary.

The exclusion criteria describe other medications that are prohibited during this study. There are no prohibited therapies during the post-treatment follow-up phase.

9.6.2 Pembrolizumab

Medications or vaccinations specifically prohibited in the exclusion criteria are not allowed during the ongoing trial. If there is a clinical indication for one of these or other medications or vaccinations specifically prohibited during the trial, discontinuation from trial therapy or vaccination may be required. The investigator should discuss any questions regarding this with the Merck Clinical team. The final decision on any supportive therapy or vaccination rests with the investigator and/or the subject's primary physician.

All concomitant medications received within 28 days before the first dose of trial treatment and 30 days after the last dose of trial treatment should be recorded. Concomitant medications administered after 30 days after the last dose of trial treatment should be recorded for SAEs and ECIs.

Subjects are prohibited from receiving the following therapies during the Screening and Treatment Phase (including retreatment for post-complete response relapse) of this trial:

- Antineoplastic systemic chemotherapy or biological therapy
- Immunotherapy not specified in this protocol
- Chemotherapy not specified in this protocol
- Investigational agents other than pembrolizumab
- Radiation therapy
 - o Note: Radiation therapy to a symptomatic lesion or to the brain may be allowed at the investigator's discretion.
- Live vaccines within 30 days prior to the first dose of trial treatment and while
 participating in the trial. Examples of live vaccines include, but are not limited to, the
 following: measles, mumps, rubella, varicella/zoster, yellow fever, rabies, BCG, and
 typhoid vaccine.
- Systemic glucocorticoids for any purpose other than to modulate symptoms from an
 event of clinical interest of suspected immunologic etiology. The use of physiologic
 doses or higher of corticosteroids for non-immune mediated indications may be
 approved after consultation with the principal investigator.

Subjects who, in the assessment by the investigator, require the use of any of the aforementioned treatments for clinical management should be removed from the trial. Subjects may receive other medications that the investigator deems to be medically necessary.

The Exclusion Criteria describes other medications which are prohibited in this trial.

There are no prohibited therapies during the Post-Treatment Follow-up Phase.

10.0 EVALUATION DURING TREATMENT/INTERVENTION

10.1 - Pre-treatment diagnosis confirmation

All patients will have histological confirmation of their diagnosis prior to treatment. Baseline clinical and radiologic evaluations are to be conducted within 3 weeks of starting protocol therapy. In addition, a mandatory baseline biopsy will be performed within 3 weeks of first dose of the study drugs for all patients enrolled in the study where feasible.

10.2 - Standard evaluations

Evaluations at clinic visits will occur on day 1 (± 3 days) of cycle 1 and every cycle thereafter. The clinical evaluations are delineated further in the study calendar (Table 5) and include:

- Full medical history, physical exam, assessment of performance status by KPS or ECOG status
- Review of concomitant medications

Complete vital signs (pulse, blood pressure, temperature, respiratory rate, and oxygen saturation) as well as weight and height. Height may be documented at any time prior to registration.

All patients will undergo a baseline staging CT scan of the chest (with or without contrast), abdomen and pelvis (with or without contrast), and MRI of the affected area if deemed necessary by the treating physician. Response evaluations will occur at week 8 and every 8 weeks subsequently (± 1 week window) until 56 weeks, and then every 12 weeks thereafter or as per the discretion of the treating investigator.

Routine/standard blood samples will be obtained at screening, day 1 of cycle 1 and then prior to every scheduled treatment visit (± 3 days) thereafter. All routine blood samples should be obtained prior to the daily dose epacadostat and/or pembrolizumab. These samples will be used for routine tests and are part of standard of care. The following analyses will be assessed at various time points during the study:

Hematology: Complete blood count with differential

Chemistry: phosphorus, magnesium

Serum pregnancy test for women with child-bearing potential

Comprehensive metabolic panel (sodium, potassium, chloride, bicarbonate, calcium, glucose, blood urea nitrogen, creatinine, total protein, albumin, serum bilirubin, alkaline phosphatase, ASL, AST)

TSH, T4 free, T3

Amylase and lipase

Additional tests if clinically indicated

10.3 Required Laboratory Parameters for Treatment

A new dose of therapy may be initiated provided that the patient meets the following criteria on the day of treatment:

- ANC 1,000/µL
- Platelets> 75,000/μL
- All grade 2 non-hematologic adverse events (except for fatigue, nausea and vomiting, or laboratory values that are not clinically significant) must have resolved to CTCAE grade 1

10.4 - Tumor and blood samples for correlative/companion studies

All patients enrolled on this study will undergo paired biopsies/blood samples for research purposes (correlative/companion studies) where feasible

Blood samples for research purposes will be obtained at week 1 (before treatment), 4, 7, 13, and 22 and at the date of the off study visit (± 3 days). This is detailed in Table 5 (Study calendar). Research blood collection procedures will be performed as outlined in Appendix A.

Biopsies for research purposes will be done at baseline (within 3 weeks of the first dose of epacadostat and/or pembrolizumab) and at Week 7 in all patients enrolled in this study where feasible. Up to 6 cores from each tumor biopsy site should be taken where feasible and safe to do so. An optional biopsy will be offered to all patients at the time of progression. Biopsy procedures will otherwise be performed in accordance with institutional guidelines and the biopsy protocol outlined in Appendix A.

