 planned study therapy. Examples of live vaccines include, but are not limited to, the
 following: measles, mumps, rubella, chicken pox, yellow fever, rabies, Bacillus
 Calmette-Guerin (BCG), and typhoid vaccine. Note: Seasonal influenza vaccines
 for injection are generally inactivated flu vaccines and are allowed; however
 intranasal influenza vaccines (e.g., Flu-Mist®) are live attenuated vaccines, and are
 not allowed.
- Has a known history of active TB (Bacillus Tuberculosis)
- Is currently participating and receiving study therapy or has participated in a study of an investigational agent and received study therapy or used an investigational device within 2 weeks of the first dose of treatment.
- Has had a prior chemotherapy, immunotherapy, biological therapy, targeted small
 molecule therapy, or radiation therapy within 3 weeks prior to study Day 1 or who has
 not recovered (i.e., \$ Grade 1 or at baseline) from adverse events due to previously
 administered agent.
 - o Note: Subjects with\$ Grade 2 neuropathy, alopecia or hypothyroidism are an exception to this criterion and may qualify for the study.
 - Note: If subject received major surgery, they must have recovered adequately from the toxicity and/or complications from the intervention prior to starting therapy events due to a previously administered agent.
- Presence of a gastrointestinal condition that may affect drug absorption
- Known allergy or reaction to any component of either study drug formulation
- Women who are pregnant or breast feeding
- Subjects expecting to conceive or father children within the projected duration of the trial, starting with the pre-screening or screening visit through 120 days after the last dose of study treatment(s).
- Inability to comply with protocol required procedures

- Subjects receiving Monoamine Oxidase Inhibitors (MAOIs) or drug which has significant MAOI activity (meperidine, linezolid, methylene blue) within the 21 days before screening.
- Any history of Serotonin Syndrome (SS) after receiving serotonergic drugs.

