11.4.1 Epacadostat

Dose reductions/Interruptions - Epacadostat

In some circumstances, it may be necessary to temporarily interrupt both study treatments as a result of AEs that may have an unclear relationship to study drug. If an interruption is necessary both study treatments should be interrupted.

Any interruptions of> 2 weeks or for LFT abnormalities must be discussed with the medical monitor before resuming treatment. Treatment with both study drugs should be withheld for drug-related Grade 4 hematologic toxicities, nonhematological toxicity Grade 3 (including laboratory abnormalities), and severe or life-threatening AEs.

Epacadostat may be dose reduced according to the guidelines and dose levels described in Table 14.

Dosing interruptions may be permitted in the case of medical/surgical events or logistical reasons not related to study therapy (eg, elective surgery, unrelated medical events,

subject vacation, and/or holidays). Subjects will be placed back on study therapy within 3 weeks of the scheduled interruption. The reason for interruption should be documented in the subject's study record.

For patients who do not tolerate the RP2D of epacadostat in combination with pembrolizumab, three dose reductions are permitted (Table 14) in order to allow the patient to continue on study drug. The following guidelines need to be applied and these changes must be recorded on the Dosage Administration Record. Please refer to Table 15 for dose reduction steps and criteria for interruption and re-initiation of epacadostat for drug-related toxicities. Doses held during the study will not be made up. When toxicity that resulted in a dose reduction improves to grade 1 or less, the dose can be re-escalated at the investigators discretion provided there are no other concomitant toxicities.

Table 14 Dose Modification Algorithm for Adverse Events Associated with Epacadostat

Epacadostat Dose Levels	Dose Level 1 (starting dose)	Dose Level -1	Dose Level -2
Actual Dose	100mg bid	50mg bid	25mg bid

Table 15. Dose Modification Guidelines for Epacadostat Related Adverse Effects without Immune Etiology

Toxicity	Grade	Hold	Timing for	Dose for	Discontinue
		Treatment	Treatment	Treatment	Subject (after
		(Y/N)	Restart	Restart	discussion with PI)
Hematologic	1,2,3	No	N/A	N/A	N/A
Toxicity					
	4	Yes	Permanently discontinue treatment	N/A	Permanently discontinue study treatment
Non Hematologic Toxicity	1	No	N/A	N/A	N/A

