Note: Exception to be treated to similar Grade 1 toxicity: -G2 alopecia	2	Consider holding for persistent symptoms	Toxicity resolves to ::;; grade 1 or baseline	Restart at same dose	Toxicity does not resolve within 12 weeks of last dose of treatment
-G2 fatigue	nyestigator agre	ement subjects	Toxicity resolves to ::;; grade 1 or baseline. Subjects with AEs that stabilize at grade 2 (such as neuropathy) may resume treatment upon principal investigator approval. Permanent discontinuation of epacadostat in setting of grade 4 toxicities with the exception of grade 4 laboratory abnormalities that are deemed clinically insignificant	Restart at 1 dose level lower	Toxicity does not resolve within 12 weeks of last dose of treatment. Permanent discontinuation should be considered for any severe or life threatening event.

With principal investigator agreement, subjects with a laboratory AE still at grade 2 after 12 weeks may continue treatment in the study only if asymptomatic and controlled.

Adverse events of a potential immunologic etiology or immune-related AEs (irAEs) may be defined as an AE of unknown etiology, associated with drug exposure and consistent with an immune phenomenon. Immune-related AEs may be predicted based on the nature of the compounds, their mechanism of action, and reported experience with immunotherapies that have a similar mechanism of action. Special attention should be paid to AEs that may

be suggestive of potential irAEs. An irAE can occur shortly after the first dose or several months after the last dose of treatment.

If an irAE is suspected, efforts should be made to rule out neoplastic, infectious, metabolic, toxin, or other etiologic causes prior to labeling an AE as an irAE.

Immune-related adverse events may be attributable to epacadostat alone, pembrolizumab alone, or the combination of both agents. If the event is clearly related to one of the agents, follow the instructions specific for that agent. If the event is related to both agents, follow the action taken instructions for both.

Suggested supportive care measures for the management of adverse events with potential immunologic etiology are outlined in Table 16. below. Note that several courses of steroid tapering may be necessary as symptoms may worsen when the steroid dose is decreased.

It may be necessary to perform conditional procedures such as bronchoscopy, endoscopy, or skin photography as part of evaluation of the event.

 Table 16:

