- Treat with an initial dose of methylprednisolone 1 to 2 mg/kg intravenously followed by oral prednisone 1 to 2 mg/kg per day. When symptoms improve to Grade 1 or less, steroid taper should be started and continued over no less than 4 weeks. Replacement of appropriate hormones may be required as the steroid dose is tapered.
- Permanently discontinue for inability to reduce corticosteroid dose to 10 mg or less of prednisone or equivalent per day within 12 weeks.
- Hypophysitis with clinically significant adrenal insufficiency and hypotension, dehydration, and electrolyte abnormalities (such as hyponatremia and hyperkalemia) constitutes adrenal crisis.
- Hospitalization and endocrine consultation should be considered.

Grade 4 events:

- Discontinue pembrolizumab.
- Manage as per Grade 3

Thyroid disorders can occur at any time during treatment. Monitor patients for changes in thyroid function (at the start of treatment, periodically during treatment, and as indicated based on clinical evaluation) and for clinical signs and symptoms of thyroid disorders.

Grade 2 events (and Grade 3-4 hypothyroidism):

- Monitor thyroid function or other hormonal level tests and serum chemistries more frequently until returned to baseline values.
- Thyroid hormone and/or steroid replacement therapy to manage adrenal insufficiency.
- Therapy with pembrolizumab can be continued while treatment for the thyroid disorder is instituted.
- In hyperthyroidism, non-selective beta-blockers (e.g. propranolol) are suggested as initial therapy.
- In hypothyroidism, thyroid hormone replacement therapy, with levothyroxine or liothyroinine, is indicated per standard of care.
- Consultation with an endocrinologist may be considered.

Grade 3 hyperthyroidism events:

- Hold pembrolizumab.
- Rule out infection and sepsis with appropriate cultures and imaging.
- Treat with an initial dose of methylprednisolone 1 to 2 mg/kg intravenously followed by oral prednisone 1 to 2 mg/kg per day. When symptoms improve to Grade 1 or less, steroid taper should be started and continued over no less than 4 weeks. Replacement of appropriate hormones may be required as the steroid dose is tapered.
- Permanently discontinue for inability to reduce corticosteroid dose to 10 mg or less of prednisone or equivalent per day within 12 weeks.

Grade 4 events:

- Discontinue pembrolizumab.
- Manage as per Grade 3

A2.4 Hematologic

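### Section 10.3 bars re-dosing at unresolved grade 2 where Table 16 (thyroid events) and Table 15 (alopecia) say not to hold, and no passage says which rule prevails

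*Combined protocol and SAP*

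**What the plan says.** Section 10.3 sets criteria for each new dose: "A new dose of therapy may be initiated provided that the patient meets the following criteria on the day of treatment". Besides an ANC minimum and "Platelets> 75,000" per µL, it requires: "All grade 2 non-hematologic adverse events (except for fatigue, nausea and vomiting, or laboratory values that are not clinically significant) must have resolved", that is, to CTCAE grade 1. Alopecia, rash, neuropathy and thyroid disease are not among its exceptions.

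Section 11.4.1 gives event-specific rules. In Table 16 the action for both drugs is Continue for grade 2 hyperthyroidism, grade 2-4 hypothyroidism and grade 1-2 rash. Table 15 (epacadostat-related, non-immune effects) treats grade 2 alopecia and grade 2 fatigue as grade 1, where the hold column says no. For other grade 2 non-hematologic toxicity it says "Consider holding for persistent symptoms".

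Appendix B covers grade 2 thyroid events and grade 3-4 hypothyroidism with: "Therapy with pembrolizumab can be continued while treatment for the thyroid disorder is instituted".

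Section 6.2 requires recovery from toxicity of earlier treatment but adds that subjects with "Grade 2 neuropathy, alopecia or hypothyroidism are an exception to this criterion and may qualify for the study".

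**The concern.** Section 10.3 is written as a condition on every new dose, with its own closed list of exceptions. The tables in 11.4.1 are written as instructions for the same events and give a different answer. An investigator seeing a patient with persisting grade 2 hypothyroidism on day 1 of a cycle must either dose against 10.3 or withhold against Table 16.

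Three things are at stake:

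- **Consistency of treatment.** Two investigators, or one investigator at two visits, can act oppositely on the same event.
- **Deviation records.** The deviations text under Section 16.3.1 counts any unapproved departure from the protocol as a violation, so either act can be recorded as one.
- **Exposure.** Section 11.0 takes a patient off study treatment when a delay due to a related adverse event exceeds 6 weeks from the planned dose. A patient held under 10.3 for an event that stays at grade 2 could reach that limit, while Table 16 would have kept the patient on both drugs.

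**Working it through.** No figure in the plan needs reproducing. The check sets the rules side by side.

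**Direct contradictions (no outside source needed)**

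| Event | Section 10.3 | Other text |
|---|---|---|
| Grade 2 hyperthyroidism | no new dose until grade 1 | Table 16: continue both drugs; Appendix B: pembrolizumab can go on |
| Grade 2 hypothyroidism | no new dose until grade 1 | Table 16: continue both drugs; Appendix B: pembrolizumab can go on |
| Grade 2 alopecia, epacadostat-related | no new dose until grade 1 | Table 15: handled as grade 1, no hold |

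Table 15 names fatigue and alopecia together, but 10.3 excepts only fatigue.

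Comparison symbols were lost when the text was extracted, so 10.3 may mean exactly grade 2, or grade 2 and above. All three rows stand on either reading. On the second, grade 3-4 hypothyroidism conflicts as well.

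**Softer conflicts (other text permits dosing that 10.3 bars, so holding would satisfy both)**

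- Grade 2 rash: Table 16 says continue, but its management column allows drug interruption.
- Other grade 2 non-hematologic events: Table 15 makes holding optional.
- Events stabilized at grade 2, such as neuropathy: Table 15 lets treatment resume with the principal investigator's approval.
- Grade 3 or 4 endocrinopathy that has improved to a controlled grade 2: Table 16, note 2, allows resumption.
- Grade 2 AST or ALT present at baseline and persisting in patients with liver metastases: the Table 16 footnote allows continuation. This conflicts only if the value is judged clinically significant; otherwise 10.3's laboratory exception covers it.

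**Baseline conditions.** Section 6.2 lists grade 2 neuropathy, alopecia and hypothyroidism as exceptions to recovery from adverse events of earlier agents, so it treats them as adverse events. Read that way, such a patient is eligible but fails 10.3 on day 1. Against this, Section 11.1.1 leaves out of the AE definition pre-existing conditions that do not worsen, and Section 11.6.1 collects AEs only from the first dose. The point is arguable.

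**Hematologic toxicity (conditional).** The Table 15 row reads "Hematologic 1,2,3 No N/A", meaning no hold for grades 1-3. This conflicts with 10.3 only if an ANC below 1,000 or platelets at or below 75,000 can be grade 3 or lower. The documents do not print the CTCAE cut-offs, so nothing here rests on it.

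**Scale among 30 patients (expected number = 30 × rate)**

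- Hypothyroidism, all grades, Table 8: 30 × 0.048 = 1.4. The count beside that percentage reads 16 of 543, which is 2.9% and would give 0.9; this may be an extraction fault.
- Hypothyroidism, all grades, pembrolizumab series in 11.3.1: 30 × 0.083 = 2.5. The share at grade 2 is not given in either source.
- Grade 2 hyperthyroidism, same series: 30 × 2/411 = 0.15.
- Rash (softer conflict), all grades, Table 8: 30 × 0.158 = 4.7. If 25% to 50% reach grade 2 (assumed), that is 1.2 to 2.4.

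**Delay.** In the 11.3.1 series, all but two of 34 patients with hypothyroidism went on long-term replacement, and none stopped pembrolizumab for it. If a replaced patient stays graded 2 (assumption), 10.3 is never met and the 6-week limit in 11.0 is reached.

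**The case against.** The best defence is that the protocol already directs the reader to the tables. Section 9.1 refers modifications and toxicity delays to 11.4, and 11.4.2 says pembrolizumab is withheld according to Table 16. On that view 10.3 is a general screen and the event-specific rows govern. This makes an intended order plausible, but neither reference disapplies 10.3, and 10.3 carries its own exceptions without deferring to 11.4.

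Second, much of the continuing language is permissive: Appendix B offers suggestions, Table 15 says to consider holding, and the rash row allows interruption. That is correct, and it is why those items are classed as softer. It does not reach the thyroid rows of Table 16 or the alopecia note in Table 15.

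Third, 10.3's laboratory exception may cover mild thyroid-function abnormalities. It may, but not clinically significant thyroid disease, and not alopecia.

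A reader might also infer that different sites would treat patients differently. The documents do not support this: the trial is single-center, and the two other institutions named in Section 16.3 have data-analysis roles only.

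**Conclusion.** The contradiction is real for grade 2 hyperthyroidism, grade 2 hypothyroidism and epacadostat-related grade 2 alopecia. It is softer for the permissive items, arguable for conditions admitted under 6.2, and conditional for hematologic toxicity. The direct conflicts rest on no assumption beyond the events being clinically significant. On the documents' rates, thyroid events would bring the conflict to at most about two or three of 30 patients, fewer if many hypothyroidism cases are grade 1. Rash could add one or two under the assumed grade 2 share.

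A reader might infer that missed doses change who counts in the primary response analysis. That is not shown. Section 12.2 describes a cycle as 21 days with study therapy given on day 1, so a treatment-emergent event meets 10.3 at the next scheduled infusion, after the cycle 1 infusion has been given. Section 11.0 replaces patients who never receive a dose, and Section 14.1 counts an assessment missed through treatment-related toxicity as a non-response. The demonstrated consequences are inconsistent dosing, unavoidable protocol violations and possible early loss of treatment. This should be corrected, but it does not undermine the primary test.

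**What to change.** Reconcile Section 10.3 with Tables 15 and 16 and their notes, Appendix B and Section 6.2, and add one sentence stating which of them governs re-dosing. Either 10.3 lists the events for which treatment continues, or the tables are changed to match 10.3. State also whether stable baseline grade 2 conditions admitted under 6.2 count under 10.3, and check the ANC and platelet limits against the no-hold row of Table 15 using the CTCAE v4.03 grades. Which rule is right is for the clinical team to decide.

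The cost is amendment wording only. Section 16.3 describes the study as completed. If so, the practical step is to record, for reporting, which rule was applied at re-dosing visits and how the resulting departures were classified.
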